6.8.2. Prohibited Concomitant Therapies

Participants who initiate the following treatments will be discontinued from further study intervention administration and should have a final safety follow-up visit approximately 12 weeks after their last dose of study intervention:

- Immunomodulatory agents other than 6-MP, AZA, or MTX (eg, 6-thioguanine, cyclosporine, mycophenolate mofetil, tacrolimus, sirolimus, ozanimod, and JAK inhibitors).
- Immunomodulatory biologic agents (eg, TNFα antagonists, ustekinumab, vedolizumab, abatacept, anakinra).

- Experimental IBD medications (eg, etrolizumab, brazikumab, mirikizumab, risankizumab) or other investigational medications/therapies.
- Thalidomide or related agents.

The sponsor must be notified as soon as possible of any instances in which prohibited therapies are administered or planned to be administered.

Participants must not receive guselkumab outside of the protocol or participate in any other clinical study with an investigational agent while in this study and must terminate study participation if they do. Prior to termination of study participation, participants should complete evaluations for an ED visit as described in Section 1.3.

6.8.3. Vaccinations (including COVID-19)

Participants must not receive a live virus, live bacterial, or BCG vaccination during the study and for 12 weeks after receiving the last dose of study intervention.

When considering use of locally-approved (including emergency use-authorized) COVID-19 vaccines in study participants, consider protocol life style considerations (Section 5.3) and follow applicable local vaccine labeling, guidelines, and standards of care for patients receiving immunetargeted therapy. Additionally, it is recommended that, where possible, vaccine and study intervention be administered on different days, separated by as large an interval as is practical within the protocol.

7. DISCONTINUATION OF STUDY INTERVENTION AND PARTICIPANT DISCONTINUATION/WITHDRAWAL

If a participant discontinues study intervention or withdraws from the study before the end of the study, assessments should be obtained as specified in the SoA (Section 1.3).

7.1. Discontinuation of Study Intervention

A participant who discontinues study intervention will not be automatically withdrawn from the study (see Section 7.2).

A participant's study intervention must be discontinued if:

- The participant withdraws consent to receive study intervention.
- The investigator believes that for safety reasons or tolerability reasons (eg, AE) it is in the best interest of the participant to discontinue study intervention.
- The participant becomes pregnant or plans a pregnancy within the study period. Refer to Appendix 8 (Section 10.8), Contraceptive and Barrier Guidance.
- The participant initiates treatment with a prohibited therapy (Section 6.8.2).
- The participant receives a live viral, live bacterial, or BCG vaccination.
- The participant has a colectomy.

- The participant develops an opportunistic infection as determined by the investigator.
- The participant meets ANY of the following TB related conditions:
 - A diagnosis of active TB is made.
 - A participant has symptoms suggestive of active TB based on follow-up assessment questions and/or physical examination or has had recent close contact with a person with active TB and cannot or will not continue to undergo additional evaluation.
 - A participant undergoing evaluation has chest imaging with evidence of current active TB and/or a positive IGRA test result, unless active TB can be ruled out and appropriate treatment for latent TB can be initiated prior to the next administration of study intervention and continued to completion. Indeterminate/borderline results should be handled as outlined in Section 8.2.11.
 - A participant receiving treatment for latent TB discontinues this treatment prematurely or is noncompliant with the therapy.
- The participant has a serious adverse reaction that is temporally related to an injection resulting in bronchospasm with wheezing and/or dyspnea that requires ventilatory support **OR** that results in symptomatic hypotension with a decrease in systolic blood pressure >40 mm Hg or blood pressure <90/60 mm Hg.
- The participant has a reaction resulting in myalgia and/or arthralgia with fever and/or rash (suggestive of serum sickness and not representative of signs and symptoms of other recognized clinical syndromes) occurring 1 to 14 days after an injection of study intervention. These may be accompanied by other events including pruritus, facial/hand/lip edema, dysphagia, urticaria, sore throat, and/or headache.
- The participant has a malignancy including squamous cell skin cancer. Consideration may be given to allowing participants who develop ≤2 localized basal cell skin cancers that are adequately treated with no evidence of recurrence or residual disease to continue to receive study intervention.
- The participant has severe liver test abnormalities that are not transient and are not explained by other etiologies, as described in Section 8.2.4 and Appendix 10 (Section 10.10; Guideline Algorithm for Monitoring, Assessment and Evaluation of Abnormal Liver Tests).

Discontinuation of a participant's study intervention must be strongly considered under the following conditions:

- Persistent inadequate response or worsening of UC based on signs, symptoms, and/or laboratory values. If the participant experiences AEs consistent with clinically significant worsening of UC at any time during the study, these events should be evaluated by the investigator and the study medical monitor to decide on discontinuation of study intervention. Discontinuation of study intervention should be considered in participants with clinically significant worsening of UC where continuation of the study intervention is not in the best interest of the participant.
- The participant develops a serious infection, including but not limited to sepsis or pneumonia.

 Note: Any serious infection should be discussed with the medical monitor or designee, and study intervention should be withheld until the clinical assessment is complete.

on a post-baseline col assessment. If a participant can be adequately treated with psychotherapy and/or pharmacotherapy based on an evaluation by a mental health professional, then the participant, at the discretion of the investigator, may be continued with treatment if agreed to by the medical monitor or designee. Discussion of such participants with the medical monitor or designee is required.

• The participant develops a severe injection-site reaction.

If a participant discontinues study intervention for any reason before the end of the treatment period, then the assessments as specified in the SoA (Section 1.3) must be obtained. If the reason for discontinuation of study intervention is withdrawal of consent, every effort should be made to conduct the ED visit assessment, as indicated in the SoA, prior to terminating the study participation. After termination of study participation, no additional assessments are allowed. Study intervention assigned to the participant who discontinued study intervention may not be assigned to another participant. Additional participants will not be entered to replace participants who discontinue study intervention or withdraw from the study.

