Hypersensitivity reactions, including serious hypersensitivity	Serious hypersensitivity reactions including anaphylaxis have been	• Participants with known allergy, hypersensitivity, or intolerance to guselkumab or its excipients will be excluded from the study (Section 5.2).
reactions.	reported in postmarketing experience with guselkumab in psoriasis patients.	Sites are instructed that before any administration of study intervention, appropriately trained personnel and medications (eg, injectable

CONFIDENTIAL – FOIA or other similar exemptions apply

		Mitigation Strategy
Potential Risks of Clinical Significance	Summary of Data/ Rationale for Risk	5 5.
		epinephrine) must be available to treat hypersensitivity reactions, including anaphylaxis. In addition, all participants must be observed carefully for signs and symptoms of a hypersensitivity reaction (eg, urticaria, itching, hives) (Section 8.2.9).
		 Any participant who develops a serious hypersensitivity reaction such as anaphylaxis must discontinue study intervention (Section 7.1).
Malignancy	The preponderance of preclinical data suggests that blockade of endogenous IL-23 would not be detrimental and may in fact be beneficial in tumor immunosurveillance and host protection; however, a risk of malignancy cannot be excluded.	 Those participants who currently have a malignancy or have a history of malignancy within 5 years prior to screening (with exceptions noted in Section 5.2) will be excluded from the study. Additionally, participants who have a history of lymphoproliferative disease, including lymphoma; a history of monoclonal gammopathy of undetermined significance or signs and symptoms suggestive of possible lymphoproliferative disease, such as lymphadenopathy or splenomegaly will be excluded from the study (Section 5.2). During the conduct of the study, participants will undergo regular clinical monitoring including routine safety labs to assess for any changes in health status that may indicate a possible malignancy. Participants who develop a malignancy during the study (with the exception of no more than 2 localized basal cell skin cancers that are treated with no evidence of recurrence or residual disease) will be discentificated from study intervention.

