8.2.9. Hypersensitivity Reactions

Before any administration of study intervention at the study site, appropriately trained personnel and medications (eg, injectable epinephrine) must be available to treat hypersensitivity reactions, including anaphylaxis. All participants must be observed carefully for signs and symptoms of a hypersensitivity reaction (eg, urticaria, pruritis, angioedema, wheezing, dyspnea, or hypotension).

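### The risk table cites Section 7.1 for a mandatory stop after any serious hypersensitivity reaction, but Section 7.1 has no such criterion and leaves some of these reactions to investigator judgement

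*Protocol*

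**What the plan says.** Protocol Section 2.3.1, hypersensitivity row, gives this as a mitigation: "Any participant who develops a serious hypersensitivity reaction such as anaphylaxis must discontinue study intervention (Section 7.1". The only threshold is that the reaction is serious.

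Protocol Section 7.1 opens its compulsory list with "A participant's study intervention must be discontinued if". Three entries on that list bear on reactions:

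- The acute-reaction entry has two limbs. One is a "serious adverse reaction that is temporally related to an injection resulting in bronchospasm with wheezing and/or dyspnea that requires ventilatory support". The alternative is a reaction "that results in symptomatic hypotension with a decrease in systolic blood pressure >40 mm Hg or blood pressure <90/60 mm Hg".
- The delayed-reaction entry covers muscle or joint pain with fever and/or rash, 1 to 14 days after an injection, that is "suggestive of serum sickness and not representative of signs and symptoms of other recognized clinical syndromes".
- A general entry applies when the investigator believes that "for safety reasons or tolerability reasons (eg, AE) it is in the best interest of the participant to discontinue study intervention".

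Section 7.1 also has a list of conditions under which stopping must be strongly considered. Its readable text includes severe injection-site reactions, but neither hypersensitivity nor anaphylaxis.

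Protocol Section 8.2.9 covers observation and readiness to treat: "All participants must be observed carefully for signs and symptoms of a hypersensitivity reaction (eg, urticaria, pruritis, angioedema, wheezing, dyspnea, or hypotension". It contains no stopping rule.

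**The concern.** Section 2.3.1 records that serious hypersensitivity reactions, including anaphylaxis, have been reported with guselkumab after marketing, and it offers the compulsory stop as part of the answer. Section 2.3.3 then rests the favourable benefit-risk conclusion on the measures taken to minimise risk. If the section cited for one of those measures does not contain it, the assessment relies on a rule that is missing from the list of stopping criteria.

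The practical risk is inconsistency. Two sites could handle the same serious reaction differently, one following the risk table and the other following 7.1 and its own judgement. There is also a secondary effect on the analysis. SAP Section 5.6.2 plans risk-difference tables for adverse events leading to discontinuation. SAP Table 6 counts most discontinuations, including those for adverse events, as non-response. Which passage a site followed could therefore change how a participant is counted.

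**Working it through.** No arithmetic applies. The check is whether the cross-reference from 2.3.1 leads to an equivalent rule in 7.1.

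**Step 1: does the cross-reference work for other risks?** It does. The malignancy and liver-injury rows of 2.3.1 each cite 7.1 and match an entry in its compulsory list. The serious-infection row calls for stopping to be strongly considered, and 7.1 says the same. The hypersensitivity row has no counterpart, so the mismatch is not a drafting convention of the table.

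**Step 2: run illustrative serious reactions through both sections.** Each is assumed to follow an injection, to be judged a hypersensitivity reaction, and to be serious under the Appendix 7 definition, for instance because of hospitalisation.

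| Reaction | Section 2.3.1 | Event-specific criterion in Section 7.1 |
|---|---|---|
| Bronchospasm with dyspnea, ventilatory support needed | Stop | Stop |
| Symptomatic hypotension within the stated limits | Stop | Stop |
| Serum-sickness-like, day 1 to 14 | Stop | Stop |
| Bronchospasm with wheeze, no ventilatory support | Stop | Depends on how the sentence is read |
| Angioedema with generalised urticaria, no bronchospasm, no such hypotension | Stop | None |

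**Step 3: the ambiguous row.** In the respiratory limb, the words about ventilatory support may qualify the whole bronchospasm phrase or only the dyspnea. On the second reading, bronchospasm with wheeze already meets the criterion. The point therefore should not rest on a wheeze example.

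**Step 4: the last row.** Angioedema and urticaria are both signs that 8.2.9 tells sites to watch for, so this presentation is one the protocol itself anticipates. Under 2.3.1 the event alone triggers the stop. Under 7.1 the only entry that can apply is the general one, which is triggered by the investigator's belief. A rule triggered by an event and a rule triggered by judgement can give different results for the same participant.

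**The case against.** The strongest reply is that the protocol is one document. Section 2.3.1 is current text and is compulsory, so the stop is already required wherever it is printed. Section 7.1 does not describe its list as exhaustive, and its general safety entry makes stopping compulsory once the investigator reaches that view. Much of this stands. A reader might infer from 7.1 that a participant with anaphylaxis may be dosed again within protocol. The documents do not support that: further dosing would breach 2.3.1, and nothing in 7.1 authorises it. The reply does not remove the mismatch, because 2.3.1 attributes its rule to a section that does not state it.

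A reader might also see a second conflict over home dosing, because 2.3.1 asks for readiness before any administration while 8.2.9 begins "Before any administration of study intervention at the study site, appropriately trained personnel". That is weak. The sentence in 2.3.1 is an instruction to sites and cites 8.2.9, which states the scope. Section 6.1.1 separately tells participants dosing at home to contact the investigator promptly about signs of an allergic reaction.

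Two further objections limit the claimed impact. No passage says that sites consult 7.1 in preference to the risk table. It is a reasonable assumption, because 7.1 is the section on discontinuation and 2.3.1 itself points there. And SAP Section 5.6.2 lists participants with anaphylaxis or serum sickness without making discontinuation a condition, so within the SAP's scope through Week 48 those events would not disappear from the report.

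**Conclusion.** The plan is wrong as written on this point. A stated safety mitigation cites a stopping list that does not contain it, and at least one presentation the protocol anticipates requires a stop under 2.3.1 but meets no event-specific criterion in 7.1. It is an internal inconsistency and does not authorise re-dosing.

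Its size cannot be given as a number. The documents state no rate of serious hypersensitivity, and the affected cases are only those outside the two acute limbs and the serum-sickness-like entry. Any effect on the discontinuation tables or on responder status is possible but cannot be estimated. The importance lies in the potential seriousness of each event and in dosing that continues up to Week 248, even though Section 10.6.4 says recruitment has stopped.

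The conclusion assumes that serious in 2.3.1 has its Appendix 7 meaning, and that the part of the strongly-considered list that cannot be read contains no hypersensitivity entry; the surrounding text there concerns mental-health assessment. It should be corrected, but it does not threaten the primary analysis.

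**What to change.** Reconcile Sections 2.3.1 and 7.1 so that the mitigation and the stopping list it cites state the same discontinuation criterion for serious hypersensitivity and anaphylaxis. The sponsor's clinical team decides which version stands; this review takes no position on that. When the text is revised, state what the ventilatory-support wording in 7.1 qualifies, so that the criterion has one reading.

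The cost is one or two sentences in the next amendment and a notice to sites, with no added visits, procedures or data collection. Under Section 10.6.1 a protocol clarification communication may be used only if study conduct does not change, and it cannot take the place of an amendment. The sponsor should decide which route applies once it has settled the criterion.

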7.2. Participant Discontinuation/Withdrawal From the Study

A participant will be withdrawn from the study for any of the following reasons:

- Lost to follow-up
- Withdrawal of consent
- Death
- Sponsor decision (eg, participating in any other clinical study with an investigational agent)

When a participant withdraws before study completion, the reason for withdrawal is to be documented in the CRF and in the source document. If the reason for withdrawal from the study is withdrawal of consent then no additional assessments are allowed.

Withdrawal of Consent

A participant declining to return for scheduled visits does not necessarily constitute withdrawal of consent. Alternate follow-up mechanisms that the participant agreed to when signing the consent form apply (eg, consult with family members, contacting the participant's other physicians, medical records, database searches, use of locator agencies at study completion,) as local regulations permit.

7.2.1. Withdrawal From the Use of Research Samples

Withdrawal from the Use of Samples in Future Research

The participant may withdraw consent for use of samples for research (refer to Long-Term Retention of Samples for Additional Future Research in Appendix 6, Regulatory, Ethical, and Study Oversight Considerations). In such a case, samples will be destroyed after they are no longer

needed for the clinical study. Details of the sample retention for research are presented in the main ICF and in the separate ICF for optional research samples.

7.3. Lost to Follow-up

To reduce the chances of a participant being deemed lost to follow-up, prior to randomization attempts should be made to obtain contact information from each participant, eg, home, work, and mobile telephone numbers and email addresses for both the participant as well as appropriate family members.

A participant will be considered lost to follow-up if the participant repeatedly fails to return for scheduled visits and is unable to be contacted by the study site. A participant cannot be deemed lost to follow-up until all reasonable efforts made by the study site personnel to contact the participant are deemed futile. The following actions must be taken if a participant fails to return to the study site for a required study visit:

- The study site personnel must attempt to contact the participant to reschedule the missed visit as soon as possible, to counsel the participant on the importance of maintaining the assigned visit schedule, to ascertain whether the participant wishes to or should continue in the study.
- Before a participant is deemed lost to follow-up, the investigator or designee must make every reasonable effort to regain contact with the participant (where possible, 3 telephone calls, e-mails, fax, and, if necessary, a certified letter to the participant's last known mailing address, or local equivalent methods). These contact attempts should be documented in the participant's medical records.
- Should the participant continue to be unreachable, they will be considered to have withdrawn from the study.

Should a study site close, eg, for operational, financial, or other reasons, and the investigator cannot reach the participant to inform them, their contact information may be transferred to another study site if feasible.

8. STUDY ASSESSMENTS AND PROCEDURES

Overview

The SoA (Section 1.3) summarizes the frequency and timing of scheduled visits, and the timing of efficacy, safety, PK, immunogenicity, PRO, and other assessments applicable to this study.

The visit window should be ± 4 days for each visit up to and including Week 12; after Week 12 to Week 24, the visit window should be ± 7 days, after Week 24 to the end of study the visit window should be ± 10 days (as described in the SoA). All post-randomization visits should be scheduled relative to the participant's randomization date. If a study visit cannot be held within the recommended visit window, the subsequent visit should be conducted as closely as possible to the study visit schedule and the site should bring the participant in gradually closer to the expected visit date by applying the allowable \pm visit window.

All PRO assessments should be conducted/completed before any tests, procedures, or other

consultations to prevent influencing participant responses. Refer to the PRO completion guidelines for instructions on the administration of PROs.

The column should be completed after all PRO assessments and before any other tests, procedures, or other consultations to prevent influencing participant perceptions.

Blood collections for PK and PD assessments should be kept as close to the specified time as possible. Other measurements may be done earlier than specified time points if needed. Actual dates and times of assessments will be recorded in the source documentation and eCRF.

For women of childbearing potential only, additional urine pregnancy tests may be performed, as determined necessary by the investigator or required by local regulation, to establish the absence of pregnancy at any time during the participation in the study.

Screening

The screening period is up to 8 weeks duration before randomization. After written informed consent has been obtained, all screening evaluations (eg, laboratory test results, clinical data, and concomitant medication data) that establish participant eligibility will be performed by the principal investigator or designee to confirm that the participant satisfies all inclusion criteria and does not violate any exclusion criteria. Participants who meet all of the inclusion and none of the exclusion criteria can be randomized in the study. Every effort should be made to adhere to the SoA (Section 1.3) for each participant. The collection of AEs will start at the time informed consent is obtained.

Diaries and/or instructions for use of a personal device will be provided to each participant. A diary will be completed from recall at screening and will be used to assess the participant's eligibility for further screening and to train the participant on the use of the diary. Participants with a combined stool frequency and combine

Participants will be instructed to complete the **ECI** and **ECI** and daily diary entries for the 10 days immediately before Week 0 through Week 4, and for the 10 days immediately before each visit thereafter, as per SoA (Section 1.3).

The screening endoscopy should be performed within 2 weeks (and at least 4 days) before the baseline visit. Participants who are identified as being at increased risk for colon cancer (Section 5.1, Inclusion Criterion 6) or for adenomatous polyps (Section 5.1, Inclusion Criterion 7) will undergo a full colonoscopy instead of a sigmoidoscopy to allow screening for dysplasia or to assess for the presence of adenomatous polyps, respectively. Any screening colonoscopy for malignancy should include surveillance biopsies consistent with local practice. At least 48 hours should elapse between a colonoscopy with polypectomy and the Week 0 visit. Local pathology results from the screening endoscopy must be reviewed before the first dose of study intervention.

Sample Collection and Handling

The actual dates and times of sample collection must be recorded in the CRF or laboratory requisition form.

Refer to the SoA (Section 1.3) for the timing and frequency of all sample collections.

Instructions for the collection, handling, storage, and shipment of samples are found in the Laboratory Manual that will be provided. Collection, handling, storage, and shipment of samples must be under the specified, and where applicable, controlled temperature conditions as indicated in the Laboratory Manual.

The total blood volume to be collected from each participant will be approximately 326 mL.

Study-Specific Materials

The investigator will be provided with the following supplies:

- Investigator Site File (includes protocol and IB)
- ICF
- IFU
- IPPM
- IWRS manual
- Participant diaries (and/or instructions for use of a personal device) and study medication diaries
- eCRF completion instructions
- Central laboratory manual
- Laboratory kits
- Biopsy manual
- Endoscopy kit
- Imaging manual
- Electronic patient-reported outcome equipment
- Patient recruitment materials
- At home stool collection kits
- Ancillary supplies as required

[figure not shown]
